We propose to conduct a randomized controlled trial (RCT) investigating a novel neurosteroid intervention in Gulf War Veterans with GWVI. Research participants will be recruited via Durham VA IRB-approved local advertising (flyers), Durham VA IRB-approved letters (and follow-up phone calls utilizing a Durham VA IRB-approved phone script), Vet Centers, and the VISN 6 MIRECC Post-Deployment Mental Health Data Repository (over 95% of these Registry participants have provided permission to be re-contacted for future research studies; over a quarter of Veterans in this OEF/OIF/OND era Registry are also Gulf War era Veterans), and by referral from the Durham VA, Raleigh CBOC, Greensboro CBOC, and Morehead City CBOC medical and behavioral health care providers. The target number of participants for this study is 140 subjects who complete at least 4 weeks of the study post-randomization (70 subjects per group, randomized to either adjunctive pregnenolone or placebo). Based on our prior investigations with pregnenolone, we conservatively estimate a drop-out rate of 30%. The power analysis for this study in GWVI was conducted under the assumption that 140 participants reach Visit 4 of the study (i.e. 4 weeks post-randomization). With an estimated 30% drop-out rate, we thus anticipate that we will have to randomize approximately 200 participants to achieve this goal.

Enrolled subjects will be 1). Veterans deployed to the Gulf War theater of operations between 1990 and 1991, 2). Gulf War Veterans who report at least 2 of the following 3 symptoms that began in 1990 or thereafter, that have lasted for more than 6 months, and that are present at the time of screening: a) fatigue that limited usual activity, b) musculoskeletal pain involving 2 or more regions of the body, c) cognitive symptoms (memory, concentration, or attentional difficulties by self-report, 3) on a stable medication regimen (no change in past 4 weeks) and no anticipated change in medications during study, 4) Able to provide informed consent for study participation. Only Gulf War era Veterans will be enrolled into this study. There will be no non-Veteran participants enrolled in this study.

RECRUITMENT PROCEDURES

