We will assess this hypothesis in the context of a two factor repeated measures mixed model ANOVA, with one between subjects factor with two levels (pregnenolone vs. placebo) and one within subjects factor with three levels (Weeks 0, 4, 8 of treatment post-randomization, which correspond to Visits 2, 4, and 6). This hypothesis will be tested using the treatment-by-time interaction, followed by contrasts in least squares means. These contrasts will examine the difference between the treatments at Weeks 4 and 8 on the changes between least squares means between Week 0 to Week 4, and Week 0 to Week 8 of treatment post-randomization. We will perform several such analyses, one for functional outcome as assessed by the Physical Component of the SF-36 (primary endpoint), and others for secondary endpoints, including: pain symptoms (as assessed by the Brief Pain Inventory), executive functioning (as assessed by the Tower of London test of the BACS), fatigue (as assessed by the Multidimensional Fatigue Inventory), and overall psychological functioning (as assessed by the Global Severity Index of the SCL-90R). The response variable will be change from baseline, and we will use baseline as a covariate. Exploratory outcomes will include the BACS composite score (cognitive symptoms), resilience (as assessed by the Connor-Davidson Resilience Scale), anxiety and depression symptoms (as assessed by the Hospital Anxiety and Depression Scale), PTSD symptoms (as assessed by the PTSD Symptom Checklist), and depression symptoms (as assessed by the Beck Depression Inventory-II scale).

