8. At Visit 6 (=8 weeks post-randomization), the study medication will be tapered (150 mg BID x 2 days, followed by 50 mg BID x 2 days, followed by study medication discontinuation). Subjects will return 1-2 weeks after Visit 6 for a follow-up visit that includes vital signs, laboratory tests, administration of the CSSRS to assess for suicidality, and adverse event assessment.

9. The WRAT, HADS, and TBI screen will be administered at Visit #1. The SF-36, BAC-A, BPI, MFI, SCL-90, HADS, BDI, PCL, WHODAS, SDS, and CDRS will be administered at Visits #2, 4 and 6. The Adverse Event Scale and CSSR (to assess for suicidality) will be administered at each in-person visit and at each telephone visit.

Randomization and Maintenance of the Blind: Randomization will occur in blocks of 10, and will be conducted by the research pharmacist at the Durham VAMC. Only the research pharmacist will have access to the randomization code during conduction of the study, and the PI and all raters, investigators and other study staff will be blinded during the study. The pharmacist does not participate in assessing any of the primary symptom or side effect dependent variables, and conveys no information about treatment assignment to subjects or staff. Study medication will be dispensed every two weeks. Subjects will be given six extra days of medication in case of a delayed or rescheduled appointment. The blind will be broken only if a medical emergency requires this information. If this occurs, the subject will be withdrawn from the study.

After the study is completed and the last participant leaves the study, the aggregate blinded data will be cleaned (i.e. reviewed for possible outliers that may reflect data entry errors, etc.) and the database will be locked. A de-identified copy of the locked data will be given to our PhD-level statistician for analysis. A de-identified copy of the locked data will also be give to a second statistician for independent replication of the study analyses. The PI will not be involved in study data analyses.

Neurosteroid Quantification:

Gas Chromatography/Mass Spectrometry (GC/MS) Preceded by High Performance Liquid Chromatography (HPLC)

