In our pilot randomized controlled trial with pregnenolone in schizophrenia (PDF attached), pregnenolone administration at the identical doses to those proposed in the current study did not significantly increase cortisol, testosterone, free testosterone, estradiol, androstenedione, or DHEA, however (Marx et al 2009, attached; please see table on p.10). A modest 20% increase was observed in DHEAS (Marx et al 2009). In this pilot study of pregnenolone in schizophrenia, as well as in subsequent investigations [specifically, a) a pilot investigation in OEF/OIF Veterans with mild TBI, b) a randomized controlled trial in schizophrenia enrolling 120 participants that was recently completed in Singapore, c) a pilot investigation in Veterans with PTSD, and d) a randomized controlled trial of 80 patients with bipolar disorder], pregnenolone was well-tolerated.

For the last several clinical studies with pregnenolone, we have quantified pregnenolone and pregnenolone metabolite levels after the trial was completed so that samples could be run in one batch with the same standard curve in order to minimize inter-assay variation. The FDA did not require monitoring of neurosteroid levels or neurosteroid metabolite levels during these studies. Neurosteroid and neurosteroid metabolite levels will thus be quantified at the completion of this study, as we have done with prior clinical investigations utilizing adjunctive pregnenolone as a pharmacological intervention.

Follow-up Plans:

Follow-up Procedures:

The follow-up plan after unanticipated withdrawal from the study (defined as withdrawal from the study at any point prior to completion and subsequent to randomization to study drug) will be to schedule a follow-up visit within 7-21 days of cessation of study participation. At this follow-up visit, patients will receive vital signs, laboratory testing (CBC, chemistry panel, liver function tests) and the Columbia Suicide Severity Rating Scale. We will also make certain that the patient has a follow-up appointment with his/her PCP or mental health care provider, and that the patient has adequate refills of psychiatric medications until the next scheduled appointment (if taking psychiatric

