Missing data: The mixed models used to evaluate the continuous response variables are able to handle moderate amounts of missing data provided they are missing at random. We will examine the missing at random assumption by assessing differences between dropouts and completers on baseline as well as response variables up to point of premature withdrawal. If the missing at random assumption does not appear to be tenable, we will report the mixed models results but spend additional effort characterizing treatment effect at time of premature withdrawal.

Statistical Computing and Programming: All statistical computing using the current version of SAS.

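### The supplied text schedules no SF-36 or secondary scale at or after withdrawal, so up to about 60 of 200 randomised participants would have a Week 0 score only, and the SAP's missing-data check and fallback have little or nothing to work with

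*Combined protocol and SAP*

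**What the plan says.** **Outcome schedule.** Study Timeline, item 9: "The SF-36, BAC-A, BPI, MFI, SCL-90, HADS, BDI, PCL, WHODAS, SDS, and CDRS will be administered at Visits #2, 4 and 6". The SAP's General Modeling paragraph confirms three assessment points for the primary and secondary measures, at the same visits. These are Weeks 0, 4 and 8 after randomisation.

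**Visit after early withdrawal.** Follow-up Plans sets a visit 7-21 days after participation ends: "At this follow-up visit, patients will receive vital signs, laboratory testing (CBC, chemistry panel, liver function tests) and the Columbia Suicide Severity Rating Scale". EKG Monitoring adds an EKG where one can be obtained, and Adverse Events Assessment adds adverse events at follow-up. All of these are safety items.

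**Expected loss.** Subject Recruitment: "The power analysis for this study in GWVI was conducted under the assumption that 140 participants reach Visit 4 of the study", and "With an estimated 30% drop-out rate, we thus anticipate that we will have to randomize approximately 200 participants to achieve this goal".

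**Analysis.** The primary-outcome text describes "one within subjects factor with three levels (Weeks 0, 4, 8 of treatment post-randomization, which correspond to Visits 2, 4, and 6"), and later in the same paragraph states: "The response variable will be change from baseline, and we will use baseline as a covariate".

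**Missing data.** The SAP relies on missing at random and will examine it by "assessing differences between dropouts and completers on baseline as well as response variables up to point of premature withdrawal". If the assumption looks untenable, the mixed-model results are still reported, with extra work to describe the treatment effect as it stood when participants left. No other sensitivity analysis is named.

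**The concern.** The SAP's safeguards need outcome scores that, on the supplied text, the protocol does not collect. The first post-baseline SF-36 is at Visit 4. The dropout allowance is for people who do not reach Visit 4. Those participants are asked back for safety checks but not for the primary endpoint.

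The comparison of pregnenolone with placebo would then rest on those who stay at least four weeks. Neither the planned check nor the fallback could show whether early leavers changed differently in the two arms. Scores not collected cannot be recovered at analysis.

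**Working it through.** **1. The plan's own figure.** Inputs from Subject Recruitment: 140 to reach Visit 4, 30% dropout. 140 / (1 - 0.30) = 200, which matches the stated number. So 200 - 140 = 60 leave before Visit 4, about 30 per arm if losses are balanced.

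**2. What each group of leavers contributes.**

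| Leaves | Outcome scores held | Missing-at-random check | Fallback at time of withdrawal |
|---|---|---|---|
| Before Visit 4 (up to about 60) | Week 0 | Baseline only | No post-baseline score |
| Between Visits 4 and 6 (number not given) | Weeks 0 and 4 | Baseline and Week 4 | Week 4 score only |

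The model description can be read with Week 0 as a response level or with change from baseline as the response. Under either reading, a Week 0 score alone says nothing about how a leaver changed.

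**3. How far leavers would have to differ (illustration, not an estimate of bias).** Assumptions: 70 observed and 30 missing per arm; placebo leavers as predicted under missing at random; pregnenolone leavers average δ points below that prediction. Two SDs are used, both from the primary power section: 12.5 (the plan's conservative choice) and 7.5 (the baseline SD it cites from earlier work in this population). The documents give no SD for change in SF-36, so either value is an assumption here.

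As a check on the set-up, 70 per arm, 7 points, SD 12.5 and two-sided alpha 0.05 give power 0.908, as in the plan's table. The standard error is 12.5 × √(2/70) = 2.113. The smallest significant difference is 1.977 × 2.113 = 4.18.

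With observed difference D:

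- Adjusted estimate = D - 0.3δ
- Variance = (2·SD² + 0.21δ²)/100 + (2·SD²/70 - 2·SD²/100), where 0.21 = 0.3 × 0.7
- Reference distribution: t with 138 df

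Example with D = 7, SD 12.5, δ = 9.1: the estimate is 7 - 2.73 = 4.27. The variance is (312.5 + 17.39)/100 + (4.464 - 3.125) = 4.638, so SE = 2.154 and t = 1.98, at the critical value.

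Value of δ at which two-sided p reaches 0.05:

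| D | SD 12.5 | SD 7.5 |
|---|---|---|
| 7 | 9.1 | 14.0 |
| 6 | 6.0 | 11.0 |
| 5 | 2.7 | 8.0 |

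**4. A natural benchmark: pregnenolone leavers lose the whole benefit (δ = D).** At SD 12.5 and D = 7, the estimate is 4.9. The variance is (312.5 + 10.29)/100 + 1.339 = 4.567, so t = 2.29 and p is about 0.023, still significant. The same formula at SD 12.5 gives p of about 0.051 for D = 6 and 0.10 for D = 5. At SD 7.5, p stays below 0.01 for all three.

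**The case against.** **The absence may only be apparent.** The Study Timeline refers to a Schedule of Events that is not in the supplied text, and an early-termination assessment could be listed there. The prose list for the follow-up visit is not exhaustive, since other sections add an EKG and adverse events. The prose is also inconsistent on scale timing: the Psychiatric Worsening rule treats PCL and BDI-II scores as available at consecutive visits two weeks apart, while item 9 schedules them four weeks apart. The SAP's fallback would itself fit with such an assessment. This stands. It limits confidence to medium and makes checking that schedule the first step. A reader might infer that the trial has no early-termination assessment at all; the supplied text cannot establish that.

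**The mixed model handles dropout.** It does so under missing at random, and the SAP says so. No check on observed data can prove that assumption, with or without extra scores. But the plan's own check has only baseline for early leavers, which is weaker than the SAP text suggests.

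**Off-drug scores answer a different question.** This also stands. If leavers do worse because they stopped the drug, the result is the effect in all randomised participants, not a bias in the planned comparison. Scores taken 7-21 days later cannot settle bias in the on-drug estimate, so they should be reported separately.

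**The 30% is conservative.** True; 60 is an upper planning figure, not a forecast.

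**The illustration can mislead.** The 2.7-point case needs both the larger SD and an observed effect below the plan's 7 points, and only the unfavourable shift is shown. Using the baseline covariate would also raise the δ values at SD 12.5. Hence both SDs and the full-loss benchmark are given.

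**Conclusion.** The concern holds on the supplied text, as a gap between what the SAP intends and what the protocol schedules. On the plan's own allowance, up to about 60 of 200 randomised participants have a Week 0 score only, and later leavers have nothing after Week 4. The missing-at-random check is reduced to baseline for the first group, the fallback has no outcome score for them, and no missing-not-at-random analysis is named.

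Two stronger readings are not supported. A reader might infer that the primary result will be biased; the documents give no reasons for leaving and no outcome data on leavers, so size and direction are unknown. At the planned 7 points and SD 12.5, even full loss of benefit in pregnenolone leavers leaves p at about 0.023. A reader might also infer that the withdrawal rules cause most of the loss; nothing in the documents says so.

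The figure of 60 assumes that the 30% falls before Visit 4, as the plan's calculation has it. The point should be addressed because the remedy is cheap and the missing scores cannot be obtained later. Confidence is medium, because the Schedule of Events was not available.

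**What to change.** **First**, check the Schedule of Events for an early-termination SF-36 and secondary scales. If they are there, state it in Follow-up Procedures and in the SAP.

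**If not:**

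1. Give the SF-36 and secondary scales on the day of withdrawal when the participant is seen, otherwise at the existing 7-21 day visit. Record the date, days off drug, blind status and reason for leaving. Use withdrawal-day scores for the SAP fallback, and report later off-drug scores separately.
2. Keep the planned model as primary and prespecify one missing-not-at-random sensitivity analysis, for example delta-adjusted over a stated range. This needs no visit and also covers those who never return.

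**Optional:** invite participants who stop drug without withdrawing consent to complete the scales at Weeks 4 and 8, for a supplementary analysis only. That would require reconciling the wording that ends study participation (the compliance rule, unblinding, serious adverse effects, psychiatric worsening) with continued outcome collection. The clinical stopping rules stay with the study team.

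**Cost.** Protocol, consent and SAP wording. Item 1 adds assessment and staff time, which the documents do not let us price; the follow-up visit is already planned and paid under Payments to Subjects. Item 2 costs analysis time only. For early leavers the optional visits cost at most 60 × 2 × $75 = $9,000, plus travel of 60 × 2 × $10 = $1,200 to 60 × 2 × $60 = $7,200. Each later leaver adds $75 plus $10-$60 travel. Some will decline or be lost, so recovery will be partial.

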3. This project will involve independent PhD-level statisticians. [name] will be completely removed from the conduction of the statistical analyses. After clinical trial data are entered by research staff, double-checked, and cleaned, the database will be locked. No statistical analyses will be conducted prior to the locking of the database. Once the data are locked, a completely de-identified copy of the dataset (no PHI) will be sent to independent statisticians. Once the de-identified database is locked, the blind will then be broken by pharmacist [name]. [name] will conduct the statistical analyses (the statistical analysis plan will be determined a priori), and this analysis will be confirmed by an independent statistician.
4. There will be a VA DSMB that will be overseeing this project.
5. [name] will promptly contact the Durham VA IRB Committee, the Durham VA R+D Committee, the VA DSMB, and the ACOS for Research at the Durham VA if a patent is issued or if a licensing agreement is negotiated.

POWER ANALYSIS: PHYSICAL COMPONENT OF THE SF-36 (Primary Endpoint).

Primary Endpoint Hypothesis: Gulf War Veterans with GWVI who were randomized to pregnenolone will demonstrate significantly greater improvements in the Physical Component Score of the SF-36 compared to Veterans randomized to placebo.

Numeric Results for Two-Sample T-Test

Null Hypothesis: Mean1=Mean2. Alternative Hypothesis: Mean1 > Mean2

The standard deviations were assumed to be equal. A prior investigation in Gulf War Veterans with GWVI determined mean baseline standard deviation in the SF-36 Physical Component Summary to be 7.5 (Donta et al 2003). We chose a more conservative SD estimate of 12.5 for this sample calculation. We utilized the baseline SF-36 score from the same investigation (Donta et al 2003) to estimate approximate baseline SF-36 scores in a Gulf War Veteran cohort with GWVI. Consistent with the literature in this area, we utilized a 7-point difference in the SF-36 as a clinically meaningful change from baseline for this sample size calculation (please see attached SF-36 scoring information in Appendix).

[figure not shown]
Power	Allocation		Alpha	Beta	Mean1	Mean2	S1	S2
	N1	N2						
0.71774	42	42	0.05000	0.28226	33.7	40.7	12.5	12.5
0.75708	46	46	0.05000	0.24292	33.7	40.7	12.5	12.5
0.79175	50	50	0.05000	0.20825	33.7	40.7	12.5	12.5
0.82211	54	54	0.05000	0.17789	33.7	40.7	12.5	12.5
0.84855	58	58	0.05000	0.15145	33.7	40.7	12.5	12.5

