Preliminary Exploration: We will explore the data using descriptive statistics and graphical techniques prior to any hypothesis testing. For categorical variables, we will examine frequency distributions and where appropriate contingency tables and histograms. For continuous variables, we will examine frequency distributions and where appropriate stem-and-leaf plots and box-and-whisker plots. When appropriate, we will consider transformation. If

necessary, due to distributional considerations, we will consider a change of analysis method to a less parametric one. For time-to-event variables, we will use Kaplan-Meier plots to obtain a global picture of the patterns in each of the treatment groups.

General Modeling: Most of our hypotheses specify continuous response variables assessed longitudinally. For those models, we will use mixed models repeated measures models. There are three assessment points for the primary and secondary outcome measures (to be administered at Visits 2, 4, and 6; each study visit is two weeks apart). We will use an AR(1) covariance structure for the repeated measures. We will fit the models preliminarily using AR(1) covariance structures and using unstructured covariance structures, and use the difference between the two -2 log likelihood functions to construct a likelihood ratio test of the advantage of the unstructured covariance structure. If the unstructured covariance structure does not fit significantly better, we will use an AR(1) structure.

We will examine group differences in least squares means at each of the major time points (Weeks 0, 4, 8 of treatment post-randomization) as described in the plans for specific hypotheses. Distributional assumptions will be examined using residuals. We recognize that it is always possible that these mixed models may fail to converge or encounter difficulties based on their use of asymptotics. In that case, we will move to analyses that assume compound symmetry, and use a Huynh-Feldt correction for the extent to which compound symmetry fails to be met.

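### The plan does not require the scale and method of the primary analysis to be fixed before the treatment codes are released

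*Combined protocol and SAP*

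**What the plan says.** Data Analysis and Statistical Considerations, item 3, sets the order of events. First, "No statistical analyses will be conducted prior to the locking of the database". The locked, de-identified data are sent to independent statisticians. Then, "Once the de-identified database is locked, the blind will then be broken by pharmacist". The analyses follow and are confirmed by a further statistician. The same item states that "the statistical analysis plan will be determined a priori".

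The Statistical Analysis Plan opens with Preliminary Exploration: "We will explore the data using descriptive statistics and graphical techniques prior to any hypothesis testing". Two options follow from that look. One is "When appropriate, we will consider transformation". The other is that, if "necessary, due to distributional considerations, we will consider a change of analysis method to a less parametric one". For time-to-event variables the same paragraph adds "Kaplan-Meier plots to obtain a global picture of the patterns in each of the treatment groups".

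The primary method is set out under Study Interventions. It is a repeated measures mixed model on the SF-36 Physical Component with baseline as covariate, tested through the treatment-by-time interaction and then contrasts at Weeks 4 and 8. The paragraph on Randomization and Maintenance of the Blind describes cleaning of blinded data before lock, aimed at data-entry errors, and keeps the PI out of the analyses.

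**The concern.** The primary outcome is continuous, so both open options reach it. An analyst who holds the codes when deciding whether to stay on the raw scale, transform, or move to a rank-type method could be influenced, knowingly or not, by how the arms compare under each choice. If the choice did respond to the arm comparison, there would be more than one chance of reaching p<0.05. The nominal two-sided 5% level assumes only one.

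The section that sets the order of events is there to manage conflict of interest in the data analysis, and its item 5 anticipates a possible patent or licence. A positive result obtained on a transformed or rank scale would be hard to defend if the record could not show that the scale was settled before anyone could see the arms.

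**Working it through.** **Order of events.** Four statements, read together:

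1. No statistical analysis takes place before lock (Data Analysis and Statistical Considerations, item 3).
2. Once the database is locked, the blind is broken, and the next sentence has the analyses conducted (same item).
3. Exploration is the first step of the SAP. Its only timing limit is that it comes before hypothesis testing (Preliminary Exploration).
4. The one review stated to be blinded is cleaning for data-entry errors, which does not choose a method (Randomization and Maintenance of the Blind).

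By 1, exploration cannot precede lock. By 2 and 3, its natural place is after the codes are released, and no sentence requires it to be earlier.

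**How open the choice is.** Other decisions in the SAP carry rules. AR(1) against unstructured covariance is settled by a likelihood ratio test. Non-convergence leads to compound symmetry with a Huynh-Feldt correction. If missing at random looks untenable, the mixed model is still reported. The transformation and the change of method have no threshold, no named transformation, no named test, and no requirement to report the planned model alongside.

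**The plan's own figure.** Inputs from the primary power analysis: 70 per arm, difference 7, SD 12.5, two-sided alpha 0.05.

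- Noncentrality = 7 / (12.5 × √(2/70)) = 3.313, with 138 degrees of freedom and critical t = 1.977.
- Exact noncentral-t power = 0.90822, equal to the stated 0.90822. The figure is correct and is unaffected by this point.

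**Size of the possible effect.** Assumptions: no treatment effect, 70 per arm, SD 12.5, a simple two-group comparison, 20,000 trials per setting. The log scale is shifted so that the smallest pooled value becomes 1. Monte Carlo standard error at 5% is √(0.05 × 0.95 / 20,000) = 0.15 percentage points.

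Choosing on results (smallest p-value kept):

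| Data | Raw t-test alone | Best of raw and rank | Best of raw, log and rank |
|---|---|---|---|
| Normal | 4.8% | 5.9% | 7.2% |
| t, 4 df | 4.8% | 6.6% | 7.3% |
| Gamma, shape 1.5 | 5.2% | 7.2% | 8.1% |

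Repeat runs with other seeds, skewed distributions and log shifts mostly gave about 7% to 8% for the last column. The lowest was 6.2%.

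Choosing on distribution only (Shapiro test, Wilcoxon if p<0.05, otherwise t-test):

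- On within-arm residuals, so with arms known: 4.9% (normal), 5.1% (t, 4 df), 4.5% (gamma, shape 2). A separate set of runs gave 4.8% to 5.4%.
- On pooled data without arm labels (10,000 trials): 5.1%, 5.2% and 4.8% (same three distribution types).

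The inflation therefore comes from choosing on the arm comparison, not from checking distributions.

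**The case against.** The strongest reply is that the plan already limits this choice. The model, factors, time points, covariate and test are specified. Exploration comes before any hypothesis test, and a change of method is allowed only on distributional grounds. A choice made strictly on those grounds costs essentially nothing in type I error, even with arms known. The PI is excluded, the statisticians are independent, and the analysis is confirmed by a second statistician. All of this stands, and it keeps the point modest. It does not close the gap. The plan fixed in advance itself leaves the choice open, excluding the PI does not blind the analyst, and confirming an analysis does not test how its method was selected.

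Three stronger readings are tempting and are not supported:

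- *That the plan states unblinding comes before exploration.* It does not. The order is inferred. The data are sent to the statisticians before the sentence on breaking the blind, so a blinded interval is conceivable. The plan does not reserve it for exploration.
- *That the by-arm displays show the primary outcome being explored by arm.* The sentence "we will use Kaplan-Meier plots to obtain a global picture of the patterns in each of the treatment groups" concerns time-to-event variables. The displays listed for continuous variables are not said to be by arm.
- *That the 5% level no longer holds.* The 7% to 8% figures require keeping the smallest p-value, which the stated criterion does not license.

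**Conclusion.** The concern holds as a potential for bias. On the natural reading of the plan, the scale and method of the primary SF-36 Physical Component analysis can be chosen with arms visible, under two options that have no trigger and no named alternative.

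Type I error stays near 5% if the choice is made on distribution alone. It reaches roughly 7% to 8% if the most favourable of three tests is kept. The upper range rests on assumed tests, distributions and log shift. All the simulations use two-sample tests rather than the baseline-adjusted mixed model, so the size is indicative only. No stated figure is wrong, and nothing in the documents suggests the freedom was misused. The change is worth making because it is cheap and lets the trial show that the method was settled without knowledge of the arms.

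**What to change.** Amend item 3 of Data Analysis and Statistical Considerations, and cross-refer from Preliminary Exploration, so that the order reads:

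1. Lock the database.
2. Send the statistician the locked data without treatment codes.
3. Explore the continuous outcomes on pooled data only, including residuals from a model without treatment.
4. Record the final scale and method for each endpoint in a dated memo.
5. Release the codes.
6. Produce any by-arm displays, including the Kaplan-Meier plots, after code release.

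Add that any later change of method is reported only as a sensitivity analysis beside the planned mixed model.

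The cost is reordered wording, one memo and a short step before unblinding. Sample size and stated power do not change.
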